- m) Known active infection or major hematologic, renal, metabolic, gastrointestinal or endocrine dysfunction in the judgment of the investigator
- n) Diagnosis of deep vein thrombosis or pulmonary embolism or major surgical procedures within 3 months prior to randomization
- o) Unreliability as a study participant based on the investigator's (or designee's) knowledge of the subject (e.g. alcohol or other drug abuse)
- p) Currently enrolled in another investigational device or drug study, or less than 30 days since ending another investigational device or drug study(s), or receiving other investigational agent(s)
- q) Female subject who has either (1) not used at least 1 highly effective method of contraception for at least 1 month prior to screening or (2) is not willing to use such a method during treatment and for an additional 15 weeks after the end of treatment, unless the subject is sterilized or postmenopausal;
 - a. Menopause is defined as: 12 months of spontaneous and continuous amenorrhea in a female \geq 55 years old or 12 months of spontaneous and continuous amenorrhea with a follicle-stimulating hormone (FSH) level > 40 IU/L (or according to the definition of "postmenopausal range" for the laboratory involved) in a female < 55 years old unless the subject has undergone bilateral oophorectomy
 - b. Highly effective methods of birth control include: not having intercourse or using birth control methods that work at least 99% of the time when used correctly and include: birth control pills, shots, implants, or patches, intrauterine devices (IUDs), tubal ligation/occlusion, sexual activity with a male partner who has had a vasectomy, condom or occlusive cap (diaphragm or cervical/vault caps) used with spermicide
- r) Subject who is pregnant or breast feeding, or planning to become pregnant during treatment and/or within 15 weeks after the end of treatment
- s) Use of a PCSK9 inhibitor within 10 weeks from screening visit
- t) Subject who has any kind of disorder that, in the opinion of the investigator, may compromise the ability of the subject to give written informed consent and/or to comply with all required study procedures
- u) Malignancy except non-melanoma skin cancers, cervical or breast ductal carcinoma in situ within the last 5 years

- v) Subject who has known sensitivity to any of the products or components to be administered during dosing

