3. STUDY DESIGN

3.1. Study Overview

This is a double-blind, randomized, placebo-controlled, parallel group Phase IV study with two treatment arms: evolocumab SC 420 mg/dL QM or matching placebo. The population will include men and women of non-child-bearing potential with documented CAD and type 2 diabetes.

Approximately 100 subjects will be screened in order to keep 40 subjects to complete the study. Subjects will be followed for 12 weeks during the treatment phase, maintaining the double-blind throughout. Assessments of ACUTE and SHORT-TERM effects of PCSK9 inhibition with evolocumab on biocellular markers of endothelial function will be measured at baseline, Week 2, and Week 12. Safety assessments will be undertaken at each study visit. Subjects whose maximally tolerated dose of statin is no type or dose (i.e. determined to be statin intolerant by primary investigator) must be randomized fairly between 2 treatment arms to prevent selection bias.

Subjects should continue on their stable dose of anti-hyperglycaemic therapies during the course of the study. However, it is important that the haemoglobin A1c (HbA1c) does not rise above 10% and that the patient does not develop severe hypoglycaemia or frequent episodes of mild-moderate hypoglycaemia, as defined by the Canadian Diabetes Association 2008 Clinical Practice Guidelines for the Prevention and Management of Diabetes.¹³

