4 SCHEDULE OF STUDY PROCEDURES

Screening assessments and study procedures outlined in this section and in Table 1 can only be performed after obtaining written informed consent.

All on-study visits and dosing should be scheduled from Day 1 (first IP administration). For example, the Week 2 visit is 2 calendar weeks after the study Day 1 visit, which corresponds to study Week 2. When it is not possible to perform the study visit at the specified time point, the visit should be performed within the visit window specified in Table 1. If a study visit is missed or late, including visits outside the visit window, subsequent visits should resume on the original visit schedule. Missed assessments at prior visits should not be duplicated at subsequent visits. With the exception of screening, all study procedures for a visit should be completed on the same day if possible.

Visit 1: Screening

- Written informed consent
- Demographics
- Medical history
- Vital signs
- 12 lead ECG measurement
- Concomitant therapy
- Dietary instruction; medication compliance reminder
- Physical examination
- Body height, waist circumference
- Body weight
- Seattle Angina Questionnaire 7 (SAQ7)
- Laboratory assessments: TSH, hematology (CBC), blood chemistry (creatinine/eGFR and electrolytes), Liver Function Tests (ALT, AST), creatinine/eGFR, HbA_{1c}, local lipid panel, urine albumin to creatinine ratio (ACR), urine pregnancy test (if female of child bearing potential)

Visit 2 (Randomization) 7-28 days after Screening

- Review for AEs/SAEs/CV events
- Concomitant therapy
- Vital signs
- Dietary instruction; medication compliance reminder
- Randomization
- Seattle Angina Questionnaire 7 (SAQ7)
- Laboratory assessments: fibrinogen, whole blood viscosity analysis, NMR lipoprotein subclass analysis, Apo B, lipoprotein (a), biocellular marker analysis, Oxidized lipid Analysis
- DNA/mRAN test for lipoprotein and inflammatory polymorphisms that may influence the response to therapy (the specimens will be stocked at site and the tests will be performed later).
- SC IP administration, QM (in-clinic) and 30 minute post-injections observation

Visit 3 (Week 2) ±4 days

- Review for AEs/SAEs/CV events
- Concomitant therapy
- Vital signs

- Dietary instruction; medication compliance reminder
- Seattle Angina Questionnaire 7 (SAQ7)

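### Section 3.1 limits women to those who cannot conceive, but 2.2(q) admits women on contraception, and their only pregnancy test is 7-28 days before the first dose

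*Combined protocol and SAP*

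**What the plan says.** **Population.** Section 3.1 (Study Overview) states: "The population will include men and women of non-child-bearing potential with documented CAD and type 2 diabetes".

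**Eligibility.** Section 2.2(q) excludes a "Female subject who has either (1) not used at least 1 highly effective method of contraception for at least 1 month prior to screening", or one who "is not willing to use such a method during treatment and for an additional 15 weeks after the end of treatment". Sterilized and postmenopausal women are exempt. Section 2.2(r) separately excludes a "Subject who is pregnant or breast feeding, or planning to become pregnant during treatment and/or within 15 weeks after the end of treatment".

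**Testing.** The Visit 1 (Screening) list in section 4 includes a "urine pregnancy test (if female of child bearing potential"). Table 1 has a matching row with a single mark, in the Screening column. No other visit has a pregnancy test in either place.

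**Timing.** Section 4 sets "Visit 2 (Randomization) 7-28 days after Screening". The first injection is given at that visit, and the other two at Weeks 4 and 8.

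**The concern.** There are two linked problems.

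First, the overview and the eligibility criteria do not describe the same women. Under 3.1 no woman who can conceive takes part. Under 2.2(q) she may, provided she uses contraception, and the schedule plans a test for her.

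Second, if she may take part, her pregnancy status is tested once, one to four weeks before she is randomized and dosed. Section 2.2(r) bars a pregnant subject, yet a site that follows the schedule exactly could randomize and inject a woman whose contraception failed after a negative screening test. At stake is an avoidable drug exposure in pregnancy. The efficacy analysis is not affected.

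**Working it through.** **Step 1: set the texts side by side.**

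| Place | What it implies for a woman who can conceive |
|---|---|
| 3.1 | Not in the population |
| 2.2(q) | Eligible if she has used, and will go on using, highly effective contraception |
| Visit 1 list, section 4 | Has a urine pregnancy test |
| Table 1 | Test row, Screening only |

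The exemption in 2.2(q) for sterilized and postmenopausal women means that the criterion has work to do only for women who can conceive. Inclusion starts at age 18, and 2.2(q) gives a menopause rule for women under 55, so younger women were in view. Three places point to admission and one to exclusion. No sentence says which prevails.

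**Step 2: count the tests.** Pregnancy tests listed at Screening: 1. Listed at Visits 2 to 6: 0. Dosing visits with a test on the same day: 0 of 3.

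**Step 3: age of the test at the first dose.** Take the first dosing visit as day 0. The section 4 interval puts Screening at day -28 to day -7. With the test done on the screening-visit day:

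- shortest: 0 - (-7) = 7 days
- longest: 0 - (-28) = 28 days

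This reproduces the plan's own 7-28 day interval. One qualification affects the lower end. Section 4 says: "With the exception of screening, all study procedures for a visit should be completed on the same day if possible". Screening procedures may therefore be spread over several days, and a test done later in that period would be fresher, at the limit 0 days old. Nothing requires that, so 28 days remains possible within the window.

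**Step 4: later doses, for context only.** Week 4 with its ±7-day window is day 21 to 35, and Week 8 is day 49 to 63.

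- Week 4: 7 + 21 = 28 to 28 + 35 = 63 days
- Week 8: 7 + 49 = 56 to 28 + 63 = 91 days

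These limits assume a test on the screening-visit day and visits within their windows. Section 4 also foresees visits outside the windows, so 63 and 91 are not absolute maxima.

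**Step 5: effect of the change.** A urine test at Visit 2 before randomization and dosing brings the age of the latest test at first dose from 7-28 days to 0.

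**The case against.** The strongest reply is that section 2 is the operative eligibility text, 3.1 is one descriptive sentence, and the schedule sides with section 2. A reader might infer that sites cannot tell whom to enrol. That goes too far: the likelier reading is a leftover phrase in 3.1. What stands is that the conflict is in the text and nothing resolves it.

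The second reply is that the risk is already low. Contraception must start at least a month before screening, with methods expected to be at least 99% reliable in correct use. Women planning a pregnancy are excluded, and adverse events are reviewed at every dosing visit. Section 3.2 randomizes only eligible subjects, so a known pregnancy already blocks entry. Other laboratory exclusions, such as eGFR, liver enzymes and HbA1c, are also checked only at Screening. All of this is fair, and it narrows the gap to an unrecognised pregnancy. It does not close it, because contraception lowers the chance of pregnancy without detecting one.

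Two further inferences are tempting and not supported:

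- **That 2.2(r) is breached at Weeks 4 and 8.** It is an entry criterion and does not govern later doses. Tests at those visits would be an extra safeguard, not enforcement of 2.2(r).
- **That the trial has no stopping, reporting or follow-up arrangements for a pregnancy on study.** The text available does not spell these out, but section 6.4 promises sites separate detailed guidelines for SAE reporting, and the consent pages are not available for review. Their absence here is not evidence that they do not exist.

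**Conclusion.** The point holds in a limited form. The conflict between 3.1 and 2.2(q) is a plain inconsistency under either reading. If women of child-bearing potential are admitted, which section 2 and the schedule favour, 2.2(r) is checked by test only at Screening, 7-28 days before the first dose under the stated window, and an unrecognised pregnancy arising in that interval would not be found by test.

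This rests on the test being done on the screening-visit day and Visit 2 falling within its window. The expected number of exposures cannot be calculated: the documents do not give the number of women concerned, which may be small in a trial planned for 40 completers and is zero if 3.1 governs. It should be corrected because it concerns participant safety and costs very little. It does not threaten the validity of the trial.

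**What to change.** Choose one population and make 3.1, 2.2(q), the Visit 1 list and Table 1 agree.

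- **If women of child-bearing potential are excluded:** amend 2.2(q) to say so, keep its menopause definition to establish who qualifies, and remove the pregnancy test from Visit 1 and Table 1. No procedure is added. The effect on the eligible pool cannot be judged from the documents.
- **If they are admitted:** delete the non-child-bearing qualifier from 3.1. Add a urine pregnancy test to the Visit 2 list and the Visit 2 column of Table 1, with a negative result required before randomization and first dose. The cost is one urine test per woman concerned, using an assay already in Table 1, at a visit she attends anyway.

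Either way a protocol amendment is needed, and the efficacy data are unaffected. Under the second option, tests before dosing at Weeks 4 and 8 are an optional addition, for a total of up to three extra tests per woman. The sponsor may also wish to write out a stop rule, pregnancy reporting, the meaning of end of treatment and a post-treatment call. Those are drafting suggestions and not part of this point.

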5 CLINICAL PROCEDURES AND SAFETY EVALUATIONS

5.1 Informed Consent

Once deemed appropriate candidates for the study, the subject will be informed of the possibility of study participation. The benefits and risks of participating in the study will be explained to the subject, and the subject will be provided an opportunity to read the informed consent form and ask any questions he/she may have. Prior to conducting any study-related procedures, the subject must provide consent to participate by signing the Institutional Review Board/Research Ethics Board (IRB/REB) approved consent form.

5.2 Demography

This includes age, sex and race.

5.3 Medical History

Data will be collected from subjects at baseline consisting of demographics, history, previous cardiac investigations, previous cardiac history, and current medication.

5.4 Physical Examination

A routine physical examination is required at Visit 1. Any abnormality must be recorded.

5.5 Vital Signs

Vital signs including blood pressure and heart rate will be recorded at the intervals indicated on the schedule of study procedures in Table 1.

5.6 ECG

A 12-lead ECG will be performed at screening visit.

5.7 Body weight, Height, and Waist Circumference

Body weight, height, and waist circumference will be recorded.

5.8 Laboratory Tests

5.8.1 Local Laboratory Tests

Local laboratory assessments include TSH, hematology, blood chemistry, liver function tests (LFTs), eGFR, HbA_{1c}, fibrinogen and urine ACR, Apo B, lipoprotein(a). Please see Table 1 for the exact schedule of all laboratory tests.

5.8.2 Additional Laboratory Tests

The following labs will be performed centrally: whole blood viscosity, lipoprotein subclass, and biocellular marker analyses. In addition, blood samples will be retained and frozen for future analysis including mRNA and DNA analysis.

5.8.3 Biocellular Marker Assessments

We will evaluate the impact on evolocumab on biomarkers of endothelial function. We will assess biomarkers of oxidative stress (MDA), inflammation (MPO), cytokines (IL-6, IL-18 and TNF- α) and vascular endothelial activation (PECAM, ICAM, VCAM and alpha5/beta 3 activations).

5.9 Concomitant Therapy

Medications are not altered for the purpose of this trial, however, any medication changes during the study must be recorded, as must those started before randomization and continued thereafter. During the hospital stay and at following study visits, changes in concomitant therapy must be recorded.

5.10 Study Drug Accounting

Double-blind study medication may only be dispensed and administered according to the study protocol by authorized personnel, as documented in the investigator's trial staff list. At each visit, compliance will be checked and recorded in the case report form.

6 MANAGEMENT OF ADVERSE EVENTS

6.1 Adverse Event (AE) Reporting

An adverse event (AE, AEs) is defined as any untoward medical occurrence in a subject who has been administered a pharmaceutical product and which does not necessarily have to have a causal relationship with this treatment. AEs include those reported spontaneously by the subject and those noted incidentally or as observed by the investigator or study staff.

Study staff will assess all AEs that occur during the period from signing of consent until end of study participation and document these in the source documents. Investigators will evaluate any changes in laboratory values and physical symptoms/signs and will determine if the change is clinically significant. If clinically significant and unexpected adverse experiences occur, they will be recorded in the case report form (CRF).

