6.3 Reporting Serious Adverse Events (SAE)

Any SAE, including death due to any cause, which occurs between enrolment and the final follow up visit whether or not related to the study drug, must be reported immediately (within 1 business day of the study site's knowledge of the event). The report will contain as much available information concerning the SAE to enable a report to be produced that satisfies regulatory reporting requirements.

The term "severe" is often used to describe the intensity (severity) of a specific event (as in mild, moderate, or severe pain); the event itself, however, may be of relatively minor medical significance (such as severe headache). By contrast, the term "serious" is used to describe an event based on an event outcome or

actions usually associated with events that pose a threat to a subject's life or functioning. Seriousness (not severity) serves as a guide for defining regulatory reporting obligations.

For all collected SAE's, the clinician who examines and evaluates the subject will determine the event's causality based on temporal relationship and his/her clinical judgment. The degree of certainty about causality will be graded using the categories below:

Definitely Related: There is clear evidence to suggest a causal relationship, and other possible contributing factors can be ruled out.

Probably Related: There is evidence to suggest a causal relationship, and the influence of other factors is unlikely.

Possibly Related: There is some evidence to suggest a causal relationship. However, the influence of other factors may have contributed to the event.

Unlikely: A clinical event, including an abnormal laboratory test result, whose temporal relationship to drug administration makes a causal relationship improbable and in which other drugs or chemicals or underlying disease provides plausible explanations

Not Related: The SAE is *completely independent of study drug administration, and/or evidence exists that the event is definitely related to another etiology.*

Pre-existing conditions should be recorded upon patient enrolment (including start date of the condition, and severity - mild, moderate, severe). After the patient signs the informed consent form, any worsening of these conditions would be recorded.

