Any new conditions would be recorded including date of onset, date of resolution, severity (mild, moderate, severe, or serious as defined above) and possible relationship to study drug or procedure. As part of the source notes, follow up clinical assessments, laboratory tests, ECGs and diagnostic imaging related to adverse event should be documented.

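### Section 6.1 restricts CRF entry to adverse events that are clinically significant and unexpected, so complete capture of non-serious expected reactions is not assured

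*Combined protocol and SAP*

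**What the plan says.** Section 3.1 commits to regular safety follow-up: "Safety assessments will be undertaken at each study visit". Section 6.1 starts with full coverage: "Study staff will assess all AEs that occur during the period from signing of consent until end of study participation" and are to "document these in the source documents". Investigators then judge whether changes in laboratory values, symptoms and signs are clinically significant. The rule for the CRF follows: "If clinically significant and unexpected adverse experiences occur, they will be recorded in the case report form (CRF").

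Section 6.3 uses different terms. A serious adverse event (SAE), "whether or not related to the study drug, must be reported immediately". For conditions present at enrolment, "any worsening of these conditions would be recorded" once consent is signed. For new ones: "Any new conditions would be recorded including date of onset, date of resolution, severity (mild, moderate, severe, or serious as defined above"), together with "possible relationship to study drug or procedure". The text on worsening and new conditions applies no test of expectedness and does not name the place of recording.

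Section 6.4 covers expedited reporting of serious unexpected adverse drug reactions (SUADRs). Section 7 describes the efficacy analysis and no analysis of adverse events.

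**The concern.** The Section 6.1 sentence is the only one in Section 6 that says which adverse events enter the CRF, and its test turns partly on expectedness. Expectedness normally decides whether a serious reaction needs expedited reporting, which is its use in Section 6.4. As a condition for data capture it can remove the reactions already known for a product. If such reactions are commoner on evolocumab, the filter would remove more events from that arm, and a CRF-based table would look more balanced than the truth.

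Section 6 defines no expected event and names no reference list, so inclusion rests on each investigator's judgement. A site following Section 6.1 and a site following the new-conditions text in Section 6.3 could build different AE datasets from the same patients. The trial is meant to support a larger one (Sections 1.1.1 and 7.1), so a gap in tolerability data would carry forward.

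**Working it through.** The plan gives no figure to reproduce here. The check is a comparison of the texts.

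**Step 1: what the Section 6.1 rule lets through.** Cross the two conditions and read the sentence literally:

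| | Clinically significant | Not clinically significant |
|---|---|---|
| Unexpected | enters CRF | source only |
| Expected | source only | source only |

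One of the four classes enters the CRF. Three need only be in source.

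**Step 2: what other text recovers.**

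- *Serious events.* Section 6.3 requires every SAE to be reported, related or not, with no test of expectedness. Expected serious reactions are covered.
- *Worsening and new conditions.* Section 6.3 has these recorded from mild upward. If this means the CRF, non-serious expected reactions are covered and Section 6.1 is contradicted. If it means source, the Section 6.1 filter stands. The text does not settle which.
- *Database.* Section 8 says that all study data are held in an electronic database. It does not say that AEs held only in source are entered.
- *Analysis.* Section 7 plans neither a table of AEs by arm nor a step to abstract AEs from source.

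The class left uncertain is the non-serious expected reaction. Non-serious, unexpected events judged not clinically significant are in the same position.

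**Step 3: where such events would be seen.** Section 4 has AEs reviewed at Visits 2 to 6, and each of the three dosing visits (Visits 2, 4 and 5) is followed by 30 minutes of observation in clinic. For the 40 planned completers, that is 40 × 3 = 120 observed dosing visits. A mild expected reaction noted in that window need not reach the CRF under Section 6.1.

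**Step 4: direction of the error.** Let p_E and p_P be the true proportions of subjects with some non-serious expected reaction on evolocumab and placebo, and let c be the fraction of those cases entered in the CRF. The trial is double-blind, so assume c is the same in both arms. The CRF then shows a difference of c × (p_E − p_P), which is closer to zero than the true difference whenever c is below 1. The documents fix none of c, p_E or p_P, so the direction can be stated but the size cannot.

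**Step 5: the severity scale.** The new-conditions sentence in Section 6.3 offers serious as a grade beside mild, moderate and severe. The same section explains that severity and seriousness are different things. Under that scale, a serious event could lose its intensity grade.

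**The case against.** A reader might infer that expected reactions never reach the database and cannot be compared between arms. The documents do not support that. Expected serious reactions are reported under Section 6.3. The text on worsening and new conditions is not confined to serious events: it grades from mild upward, and it mentions source notes only for follow-up assessments, tests, ECGs and imaging, which leaves room for the condition itself to be recorded in the CRF. All AEs are in source and could be abstracted later. This part of the objection stands, and it limits the point to non-serious events whose place of recording is unresolved.

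The Section 6.1 sentence may also be narrower than it looks. It follows a sentence on evaluating observed changes and speaks of adverse experiences rather than AEs, so it may have been meant only to decide which observed changes become CRF entries. That reading is possible, but no other sentence sends the remaining AEs to the CRF, so it does not close the gap.

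A reader might also infer that the filtered events are those most likely to differ between arms. The documents list no expected reactions to evolocumab, so this cannot be shown from them.

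Finally, this is a small signal-finding biomarker study with no planned AE table, so no stated analysis is spoiled. That is fair, and it limits the weight of the point. Safety data are nevertheless collected at every visit, and the rule for keeping them should be clear.

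**Conclusion.** The point holds in a limited form. Section 6.1 states a CRF entry rule with an undefined term. Followed as written, it can leave non-serious expected reactions in source documents only. It conflicts with Section 6.3 if that section's text on worsening and new conditions refers to the CRF; if it does not, that text fails to close the gap. A complete between-arm comparison of AEs is not assured, and CRF-based counts could understate known reactions.

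No numerical size can be given: there are no AE rates, no list of expected reactions, no stated allocation ratio and no known capture fraction. The conclusion rests on two assumptions: that sites apply Section 6.1 literally, and that any AE summary would be built from the CRF without a separate abstraction from source. The change is worth making because it costs little. The point does not touch the primary efficacy analysis.

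**What to change.** 1. **Section 6.1.** Replace the CRF sentence with a rule that every AE between consent and the end of participation is entered in the CRF, regardless of expectedness or clinical significance, with onset, resolution, severity (mild, moderate or severe), seriousness, causality and expectedness. Keep expectedness as a recorded field because Section 6.4 needs it for SUADR reporting; it should not decide entry.
2. **Section 6.3.** State that worsening of pre-existing conditions and new conditions are recorded in the CRF. Remove serious from the severity scale and record seriousness as its own field.
3. **Section 7.** Add a descriptive summary of AEs by arm. No hypothesis test is needed in a study of this kind.

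The cost is a few lines of protocol text, a check that the CRF has these fields, and a little extra entry for about 40 subjects over 12 weeks. The events are already assessed and documented in source, so no new patient contact is needed.
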